10 Statistics	22
10.1 Sample Size	22
10.2 Analysis	23
11 Direct Access to Source Data and Documents	23
12 Ethics & Regulatory Approvals	23
13 Quality Assurance	23
14 Data Handling	23
14.1 Source Data	.24
15 Data Management	24
16 Publication Policy	24

17 Insurance & Indemnity24	4
18 Financial Aspects	5
19 Signatures	5
19.1 CI Signature	5
19.2 PI Signature	5

1. Study Synopsis

Title of clinical trial	Study of the Golimumab Exposure-Response Relationship using Serum Trough Levels				
Protocol Short Title/Acronym	GO-LEVEL				
Trial Phase if not mentioned in title	Phase IV				
Sponsor name	Guy's & St Thomas' NHS Foundation Trust				
Chief Investigator	[name]				
EudraCT number	2017-001374-42				
IRAS number	194917				
Medical condition or disease under investigation	Ulcerative colitis (UC)				
Purpose of clinical trial	To study the exposure-response relationship of golimumab using serum trough levels				
Primary objective	To define a week 6 golimumab trough level concentration that predicts response at week 14				
	To define golimumab trough level concentrations at weeks 6, 10 and 14 that predict response at each time point during induction therapy, respectively.				
Secondary objective (s)	To define a golimumab trough threshold that is associated with remission during maintenance therapy.				
	Tertiary objectives will centre on the study of the relationship between serum golimumab trough levels and novel disease activity indices (PRO2), biochemical markers of disease activity (CRP, faecal calprotectin) and quality of life indices. The role of anti-drug antibodies will also be investigated in relation to trough levels and disease activity.				

Trial Design	Open-label, non-randomised, phase IV trial. Patients commencing induction therapy with golimumab (cohort 1) will be enrolled into a prospective study.					
	 Patients on maintenance golimumab therapy (coho 2) will be enrolled into a cross-sectional study. 					
	Primary: golimumab trough levels and UC disease activity (SCCAI) at weeks 6 and 10					
Endpoints	Secondary: biochemical markers of UC disease activity (fecal calprotectin and CRP), clinical disease activity (PRO2), development of antibodies and guality of life (IBD-Control) at weeks 6. 10 and 14.					
Sample Size	Total: 112 patients (cohort 1: 42 patients, cohort 2: 70 patients)					
	Inclusion criteria for cohort 1: • Aged 18 years or over • Written informed consent to participate • Moderate-to-severe UC, defined as: • SCCAI > 5 and, • A raised fecal calprotectin (> 59 μg/g) or, • A raised CRP (> 5 mg/L) or, • Endoscopic disease activity Mayo 2 or above,					
Summary of eligibility criteria	Evaluated within 4 weeks of screening					
	 Commencing golimumab treatment Sufficient English language skills to understand the patient information sheet and consent form 					
	Inclusion criteria for cohort 2:					
	 Aged 18 years or over Written informed consent to participate Receiving golimumab treatment for UC over 14 weeks (have completed 6 injections at time of screening) Sufficient English language skills to understand the patient information sheet and consent form 					

	 Exclusion criteria (cohort 1 only) Contra-indication to golimumab: tuberculosis, severe infections or congestive cardiac failure Imminent need for colectomy (i.e. colectomy is being planned) Previous primary non-response to anti- TNF therapy in the opinion of the investigator Previous treatment with more than one anti-TNF therapy (excluding golimumab) 					
IMP, dosage and route of administration	Patients will receive standard induction treatment with subcutaneous golimumab 200 mg at week 0 and 100 mg at week 2. Followed by maintenance treatment of 50 or 100 mg (based on weight) every four weeks until the supervising clinician makes the decision to withdraw treatment (as is the standard of care).					
Active comparator product(s)	N/A					
Maximum duration of treatment of a Subject	Total duration of treatment will be decided by the supervising physician on clinical grounds (exactly as the standard of care) and enrolment into the study will have no bearing on this decision.					
Version and date of protocol amendments	Version 4.1, 13 th June 2019					

2. Glossary of Terms

ADA	Anti-drug antibodies
CRP	C-reactive protein
EMA	European Medicines Agency
FDA	US Food and Drug Administration
GCP	Good Clinical Practice
PK	Pharmacokinetics
QoL	Quality of Life
RCT	Randomized controlled trial
(S)AE	(Serious) Adverse Event
Sponsor	The sponsor is the party that commissions the organization or
	performance of the research, for example a pharmaceutical
	company, academic hospital, scientific organization or investigator.
	A party that provides funding for a study but does not commission
	it is not regarded as the sponsor, but referred to as a subsidizing
	party.
SCCAI	Simple Clinical Colitis Activity Index
SUSAR	Suspected Unexpected Serious Adverse Reaction
TNF	Tumor necrosis factor
	Lileorative Colitie

3. Background & Rationale

The advent of biologic therapies has led to significant changes in treatment strategies for ulcerative colitis (UC). Prior to biologic therapies, options for treatment primarily consisted of the stepwise use of mesalazine, corticosteroids and immunomodulators for disease of increasing severity. Mesalazine was used to achieve and maintain remission in mild-to-moderate cases with the addition of corticosteroids for those failing to respond or with severe disease. Patients with colitis refractory to intravenous (IV) corticosteroids received ciclosporin or underwent colectomy. Over the past decade, multiple clinical trials have shown the efficacy of anti-TNF therapies for these patients with moderate to severe UC. Therefore, Anti-TNF agents are key tools in current treatment algorithms for both chronically active and acute severe UC.

The effectiveness of biologic agents has also changed treatment goals in ulcerative colitis. This is evident in the evolution of endpoints used for clinical trials and targets used in clinical practice. Conventional and established goals of treatment focused predominantly on achieving symptomatic remission. The cessation of corticosteroid use and achieving mucosal healing were secondary goals. However, in the era of anti-TNF agents with the ability to heal colonic mucosa when other drugs have failed, mucosal healing and steroid-free clinical remission have gained prominence as therapeutic targets.

A significant proportion of UC patients fail to respond to induction therapy with anti-TNF agents (primary non-responders) or require dose escalation due to loss of response over time (secondary non-responders). Dose escalation has been demonstrated to be an effective strategy in patients losing response to anti-TNF therapy. Where this strategy fails or in the presence of significant levels of anti-drug antibodies, switching to another anti-TNF agent (or mechanism of action) is advocated. Therefore, an increase in the range of anti-TNF agents available to clinicians was desired and necessary to overcome the substantial rates of non-response over time. In addition, a better understanding of the effect-response relationship of these agents would allow a more evidence-based approach to dose optimization.

Golimumab represents a new treatment option for patients with moderate-to-severe UC, failing or intolerant of conventional treatments. It is a transgenic, fully human monoclonal immunoglobulin G1 antibody that is synthesized from TNF-immunized transgenic mice expressing human immunoglobulin G. Although it was approved for use in rheumatoid arthritis, psoriatic arthritis, and ankylosing spondylitis in 2009, it was not until 2013 that the US Food and Drug Administration (FDA) and the European Medicines Agency (EMA) granted approval for UC.

The PURSUIT (Program of Ulcerative Colitis Research Studies Utilizing an Investigational Treatment) trial program was a series of randomized, double-blind, placebo-controlled studies that led to regulatory approval for the use of golimumab in UC^{1,2}. The comprehensive trial program consisted of investigation of the most appropriate route of administration (subcutaneous or intravenous), a phase II doseranging study and a phase III trial of induction and maintenance therapy. Subcutaneous administration was found to result in equivalent efficacy and a preferable pharmacokinetic profile when compared with intravenous dosing and is therefore the approved route of administration. PURSUIT-SC demonstrated that induction therapy with golimumab resulted in a significantly greater proportion of patients achieving a clinical response, clinical remission and mucosal healing at week 6 compared with placebo¹. All subjects from the PURSUIT-SC study were eligible for enrollment into PURSUIT-M, which evaluated the efficacy and safety of golimumab maintenance therapy over 54 weeks. On-going treatment with golimumab was shown to result in a significantly increased rate of sustained clinical benefit (both response and remission) compared with placebo².

However, despite the fact that the PURSUIT trial program yielded positive results and met its primary endpoints, unanswered questions remain regarding the optimal use of golimumab in UC. For example, how could the observed rates of primary and secondary non-response (approximately 50% and 40%) be minimized? In addition to significant rates of non-response, the majority of patients who do respond to the drug remain symptomatic to some degree, are on concomitant steroids, and are without a "normal or inactive" (Mayo 0) mucosal appearance. It's possible that these outcomes could be improved upon, given a more detailed understanding of the initial exposure-response relationship data that emerged from PURSUIT.

Patients with higher serum concentrations of golimumab were observed to have higher rates of response and remission as well as greater improvement in median composite Mayo scores. In PURSUIT-SC the change from baseline Mayo score and rates of clinical response and clinical remission at week 6 increased with increasing quartiles of serum golimumab concentration. Serum quartile analysis of the subsequent maintenance trial showed that more patients in the higher quartiles achieved clinical response through to week 54, or clinical remission at both weeks 30 and 54, when compared with those in the lower quartiles.

In a recent publication, Adedokun and colleagues reported a rigorous and meticulously performed a study of the pharmacokinetics and pharmacodynamics of golimumab using samples taken as part of the PURSUIT trials. As part of these analyses the authors found serum golimumab concentrations to be dose proportional and that a positive correlation exists between concentrations and efficacy outcomes (clinical response, clinical remission and mucosal healing) during induction and maintenance therapy. They then went further by using receiver-operating-characteristics (ROC) curve analysis to define serum golimumab concentrations that may serve as potential targets for treatment optimization; proposing thresholds of 2.5 µg/ml at week 6 and 1.4 µg/ml during steadystate maintenance therapy³. Prior to this, similar findings were also reported by a group from Leuven as part of an observational study of 21 patients being treated with golimumab in a clinical setting. Median golimumab concentrations were significantly higher in partial clinical responders than in non-responders at week 2 (10.0 vs 7.4 μ g/ml, p = 0.035) and week 6 (5.1 vs 2.1 µg/ml, p = 0.037). Their ROC curve analysis revealed a cut-off of 2.6 µg/ml at week 6 (90% specificity, 56% sensitivity, Area Under the Curve 0.79 [95% CI], p = 0.034) for the association with a partial clinical response after 14 weeks of treatment⁴. The authors of both of these studies highlighted the need for further prospective trials to validate their findings and add further validation to commercially available assays for the measurement of golimumab serum concentrations. Data such as these could be used to optimise the use of golimumab in clinical practice and inform prospective therapeutic drug monitoring trials employing trough levels to drive dosing.

Anti-drug antibodies were also detected in a small minority of patients (2.9%) in the PURSUIT trials and the majority of these (67.7%) were found to be neutralizing. Their occurrence was significantly less common in patients who were receiving concomitant

immunomodulators (1.1%) compared with patients who were not (3.8%). However, due to the low observed incidence it is difficult to draw conclusions regarding their impact on efficacy. Nonetheless, a clearer understanding of their impact on drug exposure and subsequently, disease activity would be of benefit in defining the optimal use and monitoring of golimumab.

4.1. Trial Objectives

Primary Objective

Protocol

To define a week 6 golimumab trough level concentration that predicts response at week 14.

Secondary Objectives

To define golimumab trough level concentrations at weeks 6, 10 and 14 that predict response at each time point, respectively.

To define a golimumab trough threshold that is associated with remission during maintenance therapy.

Tertiary Objectives

Tertiary objectives will centre on the study of the relationship between serum golimumab trough levels and novel disease activity indices (PRO2), biochemical markers of disease activity (CRP, faecal calprotectin) and quality of life indices. The role played by anti-drug antibodies will also be investigated in relation to trough levels and disease activity.

The role played by anti-drug antibodies will be investigated in relation to golimumab trough levels and disease activity.

This study will also generate data that can be used to validate a commercially available golimumab assay as well as a novel patient reported outcome (PRO) assessment of disease activity.

4.1.1 Primary endpoints

Drug exposure to golimumab will be evaluated using serum trough level concentrations measured using a commercially available ELISA produced by Theradiag (LISA TRACKER) at weeks 6 and 10. Clinical UC disease activity will be evaluated using SCCAI with the following definitions:

Remission	SCCAI ≤ 2
Response	SCCAI \leq 5, with a decrease by \geq 2
Relapse	SCCAI \geq 5 (following a response)

4.1.2 Secondary endpoints

UC disease activity assessments at each time point (weeks 6, 10 and 14) using PRO2, development of anti-drug antibodies, acute infusion reactions (allergic), fecal calprotectin, serum CRP measurements, albumin and QoL assessments using IBD-Control.

4.2 Trial Design

This will be an open-label, non-randomised, phase IV trial.

The study will involve two study groups:

Cohort 1 (42 patients): Patients commencing golimumab induction therapy will be included in a prospective, observational study.

Cohort 2 (70 patients): Patients receiving golimumab maintenance therapy will be included in a cross-sectional, observational study.

The study will be initiated and primarily run at Guy's and St Thomas' Hospital, a tertiary IBD referral center. To acquire sufficient patient numbers in a timely manner, patients will also be recruited from Kings College Hospital using pre-existing collaborative research links.

The planned inclusion period is estimated to be one and a half years; by which time the target of 112 patients (between the two study cohorts) will be enrolled.

4.3 Trial Flowchart

Patients in Cohort 1 (commencing induction treatment):

	Screen Visit (day -90 – day 0)	Day 0	Day 14	Day 38-42	Day 42	Day 66-70	Day 70	Day 94-98	Day 98
		Week 0	Week 2		Week 6		Week 10		Week 14
Signed Informed consent	x								
Collection of demographic and UC disease related data	x								
Review inclusion/exclusion criteria	x								
Golimumab administration (self-administered by patients)		x	x		x		х		x
Serum golimumab concentration and anti- drug antibody measurements				x		x		х	
Clinical disease activity scores (SCCAI and PRO2)	x			x		x		х	
Injection-site reaction and IBD-relevant concomitant medication review	X ¹			х		х		х	
Serum CRP and albumin measurements	x			x		x		х	
Faecal calprotectin (FC)	х			х		х		х	
Quality of life assessment (IBD-Control)	x			x		x		x	

¹ Injection site reaction review is not applicable at this visit

Patients in Cohort 2 (on maintenance golimumab treatment):

	Day 0	Screen Visit	Day 21-28	Day 28
Signed Informed consent		х		
Collection of demographic and UC disease related data		x		
Review inclusion/exclusion criteria		х		
Golimumab administration (self-administered by patients)	х			х
Serum golimumab concentration and anti-drug antibody measurements			х	
Clinical disease activity scores (SCCAI and PRO2)			х	
Injection-site reaction and IBD-relevant concomitant medication review		х		
Serum CRP and albumin measurements			х	
Faecal calprotectin (FC)			х	
Quality of life assessment (IBD-Control)			X	

5 Trial Medication

5.1 Investigational Medicinal Product

Golimumab (Simponi[®], Janssen Biotech, Inc., Horsham, PA, USA) is a sub-cutaneously administered anti-TNF agent. A homecare agreement is already in place with the golimumab supplier (MSD) and the medicine will be delivered to the patients' home in the standard manner for each site.

5.2 Dosing Regimen

Patients will receive standard golimumab induction treatment of 200 mg at week 0 and 100 mg at week 2, according to standard clinical practice. From week 6 maintenance treatment is started at 100 mg (\geq 80 kg) or 50 mg (< 80 kg) every four weeks. Treatment will be continued until the supervising clinician makes the decision to withdraw treatment (exactly as the standard of care). Enrolment into the trial will have no bearing on this decision.

5.3 IMP Risks

In the controlled period of the pivotal trials in rheumatoid arthritis, psoriatic arthritis, ankylosing spondylitis, and UC, upper respiratory tract infection was the most common adverse drug reaction (ADR) reported in 12.6% of golimumab-treated patients compared with 11.0% of control patients. The most serious ADRs that have been reported for golimumab include serious infections (including sepsis, pneumonia, TB, invasive fungal and opportunistic infections), demyelinating disorders, lymphoma, HBV reactivation, CHF, autoimmune processes (lupus-like syndrome) and haematologic reactions.

5.4 Drug Accountability

No accountability as this is part of local site standard care. As patients are being treated as part of standard care, the IMP will be supplied by the NHS (i.e. not by MSD).

5.5 Storage of IMP

A homecare plan (to teach patients how to self-administer injections) is already in place with the golimumab supplier (MSD) and the medicine will be delivered to the patients' home in the standard manner. Standard storage information will be given to patients.

5.6 IMP labelling

No labelling of the IMP will be required since it is a type A trial and the study drug will be used from commercial stock and according to its SmPC.

5.7 Subject Compliance

No specific compliance testing will be carried out but non-compliance could be deduced based on serum drug levels made as part of the trial.

5.8 Concomitant Medication

No restrictions on concomitant medications will be made.

Data regarding IBD-relevant concomitant medications **only** will be collected at each visit and recorded on the eCRF.

6 Selection and Withdrawal of Subjects

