6.1 Inclusion Criteria

Adult patients with moderate-to-severe UC with an inadequate response to, or unable to tolerate, one or more of the following conventional therapies: oral 5-aminosalicylates, oral corticosteroids, immunomodulators; or are corticosteroid dependent.

Inclusion criteria for cohort 1:

- Aged 18 years or over
- Written informed consent to participate
- Moderate-to-severe UC, defined as:
 - SCCAI > 5 and,
 - i. A raised fecal calprotectin (> 59 µg/g) or,
 - ii. A raised CRP (> 5 mg/L) or,
 - iii. Endoscopic disease activity Mayo 2 or above,

Evaluated within 4 weeks of screening

- Commencing golimumab treatment
- Sufficient English language skills to understand the patient information sheet and consent form

Inclusion criteria for cohort 2:

- Aged 18 years or over
- Written informed consent to participate
- Receiving golimumab treatment for UC over 14 weeks (have completed 6 injections at time of screening)
- Sufficient English language skills to understand the patient information sheet and consent form

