6.5 Withdrawal of Subjects

Participants in both study cohorts have the right to withdraw from the study at any time for any reason. The investigator also has the right to withdraw patients from the study drug in the event of inter-current illness, AEs, SAE's, SUSAR's, protocol violations, cure, administrative reasons or other reasons. It is understood by all concerned that an excessive rate of withdrawals can render the study un-interpretable; therefore, unnecessary withdrawal of patients should be avoided. Should a patient decide to withdraw from the study, all efforts will be made to report the reason for withdrawal as thoroughly as possible.

Should a patient withdraw from study drug *only*, efforts will be made to continue to obtain follow-up data (including relevant safety assessments), with the permission of the patient. Because this is a non-interventional trial there won't be an interim analysis or premature termination of the study.

Participants who wish to withdraw from trial medication (IMP) will be asked to confirm whether they are still willing to provide the following:

- Trial specific data (clinical and biochemical disease activity scores and quality of life evaluations)
- Data collected as per routine clinical practice

Patient status with regards continuation on the trial will be assessed at every visit and in cases of withdrawal an eCRF withdrawal form will be completed.

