8.1.1 Primary Efficacy Parameters

- Drug exposure to golimumab using serum trough level concentrations.
- Clinical UC disease activity using SCCAI using the following definitions:
 - Remission: SCCAI ≤ 2
 - Response: SCCAI \leq 5, with a decrease by \geq 2
 - Relapse: SCCAI \geq 5 (following a response)

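### Week 14 response is judged on SCCAI alone with co-medication unrestricted, so rescued golimumab failures count as responders; no rule covers patients who stop golimumab or lack a week 14 score

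*Combined protocol and SAP*

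**What the plan says.** Section 4.1 sets the primary objective: "To define a week 6 golimumab trough level concentration that predicts response at week 14". Section 4.1.1 gives the outcome rule, "Response SCCAI \leq 5, with a decrease by \geq 2", and section 8.1.1 repeats it under "Clinical UC disease activity using SCCAI using the following definitions". Neither section mentions steroids, other UC treatment or whether the patient is still on golimumab.

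Section 5.8 says "No restrictions on concomitant medications will be made", and that data on IBD-relevant medication "will be collected at each visit and recorded on the eCRF". The lead-in to section 6.1 admits patients with inadequate response or intolerance to conventional therapy and closes its list with "oral 5-aminosalicylates, oral corticosteroids, immunomodulators; or are corticosteroid dependent", so steroid use around baseline is to be expected. The flowchart in section 4.3 places cohort 1 medication reviews at screening (day -90 to day 0) and before the week 6, 10 and 14 doses. There is none at week 0.

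For patients who come off golimumab, section 6.5 says "efforts will be made to continue to obtain follow-up data", with the patient's permission. It asks whether they will still provide disease activity scores, and plans a withdrawal form and a recorded reason.

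Section 10 derives the threshold from a ROC curve. Section 10.2 compares responders with non-responders by t-test at 0.05, lists concomitant medication among the other variables, and plans univariate and bi-variate analysis of predictors of response. Sections 10 to 10.2 define no analysis population, no handling of missing data, and no classification of patients who stop treatment.

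**The concern.** The threshold is meant to say how much golimumab exposure goes with benefit from golimumab. The outcome as defined measures benefit from golimumab plus whatever else was given by week 14. A non-responder who improves on added therapy takes a non-responder's trough into the responder group, which pulls the two groups together.

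The second gap is different in kind. A patient with a week 6 trough who then stops golimumab may have no week 14 SCCAI, or may have one obtained on another drug. The plan does not say how either is classified. Someone will have to decide, in an open-label study of 42 patients, possibly with troughs and outcomes already known.

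At stake are the ROC performance, the power of the t-test, the reported response rate and, under less certain conditions, the cut-off itself.

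**Working it through.** **Plan's own figure.** Section 10.1 gives 42 patients per cohort for 80% power, two-sided, and a 2 mg/L difference, but no SD and no responder split. It cannot be reproduced, only back-solved. Section 3 cites about 50% primary non-response, so assume 21 v 21 in cohort 1:

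SD = 2 / [(1.960 + 0.842) × √(2/21)] = 2.31 mg/L.

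**Other inputs.** From the 21-patient observational study described in section 3: AUC 0.79; cut-off 2.6 µg/ml with sensitivity 56% and specificity 90%; week 6 medians 5.1 and 2.1 µg/ml. The numbers rescued or lost are assumed ranges.

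**Step 1: rescue, taken as unrelated to trough among non-responders.** If k of the 21 true non-responders are labelled responders:

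- AUC = (21 × 0.79 + k × 0.5) / (21 + k)
- sensitivity at 2.6 = (21 × 0.56 + k × 0.10) / (21 + k)
- observed trough difference = 2 × 21 / (21 + k)

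| k | AUC | Sensitivity | Difference, mg/L |
|---|---|---|---|
| 0 | 0.79 | 56% | 2.00 |
| 2 | 0.765 | 52% | 1.83 |
| 4 | 0.744 | 49% | 1.68 |
| 6 | 0.726 | 46% | 1.56 |

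Power for a rescued share of 20% (4.2 patients on average): the labelled responder group is 25.2, of whom 21/25.2 = 0.833 are true responders. The difference is 2 × 0.833 = 1.67. The responder variance is 2.31² + 0.833 × 0.167 × 2² = 5.91. The standard error is √(5.91/25.2 + 5.35/16.8) = 0.744. Power is Φ(1.67/0.744 − 1.96) = 61%. Shares of 10% and 30% give 70% and 52%.

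**Step 2: no week 14 score, taken as excluded.** If k non-responders are lost, the observed response rate is 21/(42 − k): 53%, 55% and 58% for k = 2, 4 and 6, against a true 50%. If the loss is unrelated to trough, the AUC stays at 0.79. If the lost patients come from the lower half of non-responder troughs, simulation gives 0.77, 0.75 and 0.73. Power with 10%, 20% or 30% of non-responders lost is 78%, 75% or 72%.

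**Step 3: the cut-off.** Section 10 speaks only of a trade-off between sensitivity and specificity, so the Youden index is assumed. Troughs are simulated as lognormal with medians 5.1 and 2.1, log-SD 0.778 (which gives AUC 0.79), 21 v 21.

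| Scenario | Median cut-off, µg/ml (IQR) | AUC |
|---|---|---|
| No problem | 3.15 (2.54–3.91) | 0.79 |
| 20% rescued, unrelated to trough | 3.27 (2.55–4.12) | 0.74 |
| Lowest-trough 30% of non-responders lost | 4.10 (3.26–5.14) | 0.71 |
| 20% rescued, a further 20% (lowest troughs) lost | 3.85 (3.03–4.99) | 0.68 |

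Rescue unrelated to trough dilutes discrimination and barely moves the threshold. Removing the low end of the non-responder group moves the threshold up. Rescue concentrated at low troughs would deplete the same end: with rescue confined to the lower half of non-responder troughs, simulated AUCs for k = 2, 4 and 6 fall to about 0.72–0.73, 0.66–0.67 and 0.60, and the cut-off also rises.

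**The case against.** A reader might infer that the plan drops early stoppers. It does not say so. Section 6.5 plans continued follow-up after drug withdrawal and asks for disease activity scores. What stands is narrower: that follow-up depends on effort and permission, exclusion is only the likely default for someone with no score, and no rule covers those who do give a score after stopping.

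A reader might also infer that rescue and stopping fall mainly on low-trough patients, so that the cut-off is distorted. That is plausible, but nothing in the documents shows it, and the figures in step 1 do not use it. Without it, AUC and power fall but the threshold hardly moves.

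Nor does the endpoint contradict the rationale. Section 3 says "mucosal healing and steroid-free clinical remission have gained prominence as therapeutic targets", a general remark about the field, whereas the primary outcome here is response. The remark supports the change without making the present definition an inconsistency.

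The plan does record IBD medication and lists it as a variable. That helps exploratory work but leaves every patient's label in the ROC and t-test unchanged.

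Finally, the effect is modest against sampling error. With 21 v 21, the Hanley–McNeil standard error of an AUC of 0.79 is about 0.07, and the largest shift in step 1 is 0.06. This is fair, and it is why the point is a recommended improvement and not a fatal flaw. The dilution is still systematic and avoidable by definition.

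**Conclusion.** The concern holds in two parts of unequal strength. That a rescued golimumab failure is labelled a responder follows directly from the SCCAI-only definition read with unrestricted co-medication. That patients who stop, or have no week 14 SCCAI, lack a classification rule is an omission in section 10; it is not a stated decision to exclude them.

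The size is unknown because the documents give no rescue or dropout rate. Under the assumed 21/21 split, AUC 0.79 and trough-independent rescue, 2 to 6 mislabelled patients cost about 0.03 to 0.06 in AUC. With a back-solved SD of 2.31, a 20% rescued share takes power from 80% to 61%. A material move in the threshold, such as 3.15 to 4.10 µg/ml, needs the further assumption that low-trough non-responders are selectively removed.

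**What to change.** Leave clinical care and section 5.8 as they are; the change concerns only how events enter the analysis.

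- In sections 4.1.1, 8.1.1 and 10.2, define the primary week 14 responder as a patient who meets the SCCAI response rule, is still on golimumab, and has no UC therapy (corticosteroids included) at the week 6, 10 or 14 review that is new or increased relative to the screening record. Screening is the reference because no week 0 review is scheduled.
- Class patients with a week 6 trough who stop golimumab for lack of efficacy, or have a colectomy, before week 14 as non-responders.
- State how any remaining missing week 14 SCCAI is handled.
- Report SCCAI-only response as a sensitivity analysis.
- Confirm that the eCRF captures steroid dose and start date, which the text does not specify. Screening can precede the first dose by up to 90 days, so start dates are needed to identify therapy begun between screening and week 0.

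The cost is a lower reported response rate and possibly a minor eCRF field; medication reviews and withdrawal reasons are already planned. One limit remains: a patient who stops before week 6 and has no week 6 trough still cannot enter the primary ROC, and the number of such patients should be reported.
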